### **Hypothesis**

Administration of low-level laser therapy along the skin over the mandibular body of patients who have had bilateral sagittal split osteotomy surgery for correction of the position of the mandible will reduce pain and swelling and improve neurosensory dysfunction when compared to patients who do not receive the laser treatment.

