The proposed LLLT protocol will use the Biolase Epic X, an InGaAsP diode laser (940nm) using the pain relief handpiece, a device which has received FDA approval (GUDID 00647529002537) for the treatment of pain, muscle relaxation and healing via increased local circulation. The LLLT will be administered to the experimental group at 30 j/cm^2. The laser will be applied extraorally, on the skin overlying the mandible. Application will be for 40 seconds per side, with 10 seconds administered in four places along the jawline, 1 cm apart starting from the gonial angle. The timing would coincide with standard post-operative care, with the first LLLT administration performed on post-operative day 1, prior to the patient's discharge from the hospital. The follow-up LLLT doses would be given at the standard post-op follow-up visits, at one-week intervals, which would be at week 1, week 2, week 3, week 4, week 5, and week 6. Patients will be seen for evaluation at week 8 and again at approximately 20 weeks post-surgery. The control group will follow the same post-op visit schedule, but receive a dummy treatment in which the laser handpiece is moved over the patient's jaw in a similar fashion as the experimental but without laser irradiation.

Nerve function, pain and swelling will be measured according to objective measures. A baseline measurement will be recorded pre-operatively for nerve function and pain. Baseline for swelling will be used from the final measurement at week 8, due to the changes in mandible length caused by the orthognathic surgery. Measurements for each outcome will also be performed on the days for which

LLLT is administered. The individual who performs the assessment will be blinded to the group to which each patient belongs.

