### **Outcomes (primary and secondary)**

In this study, the predictor variable was the use of laser therapy versus placebo treatment after orthognathic surgery on the mandible. The primary outcome variable was neurosensory disturbance recovery by the TPD, hard and soft sensory tests. The secondary outcome variables are pain reduction, as measured by change in VAS, and swelling reduction, as measured by soft-ruler measurement of lower face.

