### **Data analysis**

The primary outcome, change in neurosensory deficit, is measured by the three clinical tests, TPD, soft-stimulus and hard-stimulus. For TPD, the difference between the LLLT group and placebo group at each time point will be compared using an independent t-test, with alpha set at .05. The soft- and hard-stimulus tests for each region will be analyzed at each time point with a chi-square test. VAS pain score and swelling index will be analyzed using independent t-tests for the measurements on each side at each time point, with alpha set at .05. Linear regression will be performed to analyze the relationship of the pain, swelling and nerve tests with age, skeletal class, direction and magnitude of mandibular movement, and inclusion of genioplasty.

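### Pain and swelling are tested separately on left and right at every visit at 0.05 (about 34 tests), with no side, visit or summary named to decide whether either was reduced

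*Combined protocol and SAP*

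**What the plan says.** The Hypothesis section claims that laser "will reduce pain and swelling and improve neurosensory dysfunction when compared to patients who do not receive the laser treatment". It makes no distinction between left and right. Under Outcomes, "The secondary outcome variables are pain reduction, as measured by change in VAS, and swelling reduction", so both are secondary.

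Study Design randomises patients and applies the laser, or the dummy handpiece, to both sides of the jaw. It schedules "the first LLLT administration performed on post-operative day 1", then treatment at "week 1, week 2, week 3, week 4, week 5, and week 6". It adds: "Patients will be seen for evaluation at week 8 and again at approximately 20 weeks post-surgery". Outcomes are to be measured on laser days. What is measured at weeks 8 and 20 is not listed, although pain is to be rated on each side at each visit. Swelling is taped on both sides and expressed relative to a baseline length. Study Design gives that baseline as week 8 in one place and as the six-week visit in another.

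Data analysis prescribes "independent t-tests for the measurements on each side at each time point, with alpha set at .05" for both outcomes. It names no deciding side, visit or summary measure, and it gives no multiplicity rule and no way of combining the sides.

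**The concern.** When both sides get the same treatment, a left test and a right test put the same question to the same patient twice. Repeating this at each visit produces a long list of tests, any one of which could be reported as showing that pain or swelling was reduced. The two sides may also disagree on significance at the same visit, and the plan does not say which would count. At stake are the error rate behind the pain and swelling claims and some precision, because each test uses one of two available readings of the effect.

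**Working it through.** **Plan's own figure.** The Sample Size section uses a difference of 0.5, SD 0.5 and 90% power. A t-test calculation at two-sided 0.05 gives 22.02 per arm, which rounds up to the planned 23 (power 0.912 at 23). The plan does not state sidedness, but two-sided testing reproduces its figure and is assumed below. This calculation supports one two-group comparison. The plan gives no error rate for pain or swelling.

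**Number of tests.** There are nine post-operative visits: day 1, weeks 1 to 6, week 8 and about week 20.
- Pain: 9 visits × 2 sides = 18.
- Swelling: the index is zero by construction at its own baseline visit, leaving 8 visits × 2 sides = 16 with either stated baseline.
- Total: 18 + 16 = 34.
- Laser days only: 7 visits × 2 sides × 2 outcomes = 28, or 26 if the swelling baseline is week 6, which is itself a laser day.

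**False-positive chance with no true effect.** If 34 tests were independent, the chance of any p < 0.05 would be 1 − 0.95^34 = 82.5%, and of any such result favouring laser 1 − 0.975^34 = 57.7%. Repeated readings on one patient are correlated, so these serve only as reference values.

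The documents give no correlations. The simulation used 23 per arm and treated the two outcomes as independent. It assumed two sets of variance shares (patient / visit / side / residual): 0.3/0.2/0.2/0.3 and 0.6/0.1/0.15/0.15.

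| Chance of at least one false result | Range over the two sets |
|---|---|
| Pain, favouring laser | about 14-23% |
| Swelling, favouring laser | about 13-21% |
| Either outcome, favouring laser | about 26-39% |
| All 34 tests, either direction | about 48-68% |

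A wider set of assumptions (side correlation 0.3 to 0.8, visit correlation 0.3 to 0.8, correlation between outcomes 0.2) gives 22-53% for a false result favouring laser on either outcome and 42-80% for any direction. One pre-specified two-sided test per outcome would give 2.5% in laser's favour for each, and 1 − 0.975² = 4.9% for either.

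**Information lost by testing one side.** With between-side correlation r, the variance of the two-side mean relative to one side is (1 + r)/2. In the two variance sets r is patient share plus visit share: 0.3 + 0.2 = 0.5 and 0.6 + 0.1 = 0.7. The ratios are 0.75 and 0.85, so a one-side test loses 25% or 15%.

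**Power at a true 0.6 SD effect, 23 per arm, one visit.**
- One side: standardised effect 0.6, power about 51%.
- Sides averaged, r = 0.5: 0.6/√0.75 = 0.69, power about 63%.
- Sides averaged, r = 0.7: 0.6/√0.85 = 0.65, power about 58%.

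**Averaging over six weekly visits as well.** The variance of the patient mean is patient + visit/6 + side/2 + residual/12, which is 0.458 for the first set and 0.704 for the second. If the 0.6 SD effect is present at all six visits, power is about 84% and 66%. If it is present at only two of six, the mean difference is 0.6 × 2/6 = 0.2 SD and power falls to about 17% and 12%.

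**The case against.** Pain and swelling are explicitly secondary, and the sample size was built on neurosensory data. The primary outcome has a similar gap: two-point discrimination, for instance, is compared at each time point, "compared using an independent t-test, with alpha set at .05". The count of 34 depends on weeks 8 and 20 measuring both outcomes, whereas measurement is explicit only for laser days. Choosing a mean over visits rather than one named visit or a repeated-measures model is partly a matter of judgement. All this stands and limits the weight of the point. It does not remove it, because the hypothesis claims both effects and each test carries the same alpha as the primary comparison.

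Three stronger readings are tempting, and the documents do not support them.
- A reader might infer that a false finding of reduced pain or swelling is likely. The 48-68% figure includes results in which laser looks worse, and these could not support a claim of reduction. The rate favouring laser is 26-39% for either outcome in the main simulation. It is inflated, but the documents give no correlations that would show it to be likely.
- A reader might infer that each test discards half the patient's data. Both sides are measured and analysed, in separate tests. Half the information would be lost only if the sides were uncorrelated.
- A reader might credit side averaging with raising power from 51% to 66-84%. Most of that gain comes from pooling visits under a constant effect. Side averaging alone reaches 58-63%.

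**Conclusion.** The concern holds as a missing decision rule for two secondary outcomes. Read literally, the plan produces 26 to 34 side-by-visit tests of what are really two questions, and no test is named to answer either. False results favouring laser occur at about 13-23% per outcome, several times the nominal 2.5%. One-side testing also costs a moderate amount of precision, 15-25% at side correlations of 0.5 to 0.7. These sizes rest on assumed correlations, no dropout and two-sided tests. The absence of a deciding test does not depend on those assumptions. Secondary status makes this a change that should be made rather than one on which the trial's validity turns.

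**What to change.** First reconcile the swelling baseline, given in Study Design as both week 8 and the six-week visit, and state which outcomes are measured at weeks 8 and 20. Then amend Data analysis, before unblinding, as follows:
- Average left and right within each patient.
- Pre-specify one laser-minus-dummy comparison per outcome over a stated set of post-operative visits, with pain adjusted for pre-operative VAS.
- Exclude the baseline visit from the swelling summary, since the index is zero there by construction.
- Report side- and visit-specific results descriptively, with confidence intervals and no significance claims.

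This needs only a change of wording, with no extra patients, visits or measurements. There are three costs. Visit-specific p-values are no longer confirmatory. A mean over visits loses power if the effect is short-lived, so the visit window, including whether day 1 belongs in it, should be chosen and justified with that in mind. Error is held at 5% per outcome and not across both: with two independent tests the chance of any false positive is 1 − 0.95² = 9.75%.

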To evaluate nerve function, three tests will be conducted, a two-point discrimination (TPD) test, a hard stimulus test and soft stimulus test. For the TPD test, the patient will be instructed to close their eyes, and a caliper will be placed on the lateral aspect of the patient's chin. The calipers will start at 0 mm and be incrementally opened in .5mm increments, and the first distance felt by the patient as two distinct points will be recorded reported in millimeters. For the soft- and hard- stimuli tests, the lower face will be divided into eight regions, with four symmetric regions per side. Region 1 will be from the skin on the chin at the midsagittal plane laterally 1 cm. Region 2 will be the skin from the edge of Region 1 extending laterally 1 cm. Region 3 will be the skin from the edge of Region 2 extending laterally 1 cm. Region 4 will be the vermillion of the lower from the midsagittal plane to the commissure. The regions will be designated by an "L" for left or "R" for right, plus a number as per the above scheme. Each region will be checked for nerve function via two tests, a cotton-swab test and a two test. During the evaluation, the patient will be instructed to keep their eyes closed. The cotton-swab test will involve the skin in each region being lightly brushed in a 2cm vertical path twice per region, and the patient reporting if they feel the contact. Likewise, the toothpick test will involve the skin being slightly depressed by the edge of a toothpick in three spots separated by 1 cm each per region, and the patient reporting if they feel the contact. The responses will be recorded as positive or negative for soft (swab) or hard pressure (toothpick), by region.

Pain will be reported via use of a visual analogue scale (VAS). The patient will rate the intensity of the pain on each side of the mandible at each visit. The intensity of the pain will be from zero, meaning complete absence of pain, to 10, indicating the maximum amount of pain imaginable.

Swelling will be measured with a soft measuring tape from the tip of the chin to the lower lobe of the ear, bilaterally. The calculation of the swelling index will be done by subtracting the baseline length (from the six-week post-operative visit) to the measured length and dividing the difference by baseline length and multiplying by 100.

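### The covariate regression names no unit of analysis and no patient-level term for outcomes repeated within patient; if visits and sides are pooled, as the text allows, its standard errors are too small

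*Combined protocol and SAP*

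**What the plan says.** The Data analysis section gives the covariate analysis one sentence: "Linear regression will be performed to analyze the relationship of the pain, swelling and nerve tests with age", with the other factors listed as "skeletal class, direction and magnitude of mandibular movement, and inclusion of genioplasty". It does not say whether the outcome is a single visit, a change, a mean or every visit, or whether the two sides are combined. No random effect, estimating-equation method or clustered standard error is named there or elsewhere.

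The group comparisons in the same section do have a unit. For two-point discrimination (TPD), "the difference between the LLLT group and placebo group at each time point will be compared using an independent t-test". For the other continuous outcomes, "VAS pain score and swelling index will be analyzed using independent t-tests for the measurements on each side at each time point". The regression sentence carries neither limit.

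Study Design sets the repetition. Outcomes are measured on each laser day, which means post-operative day 1 and then the weekly visits, "which would be at week 1, week 2, week 3, week 4, week 5, and week 6". Evaluation visits follow at week 8 and about week 20. For pain, "The patient will rate the intensity of the pain on each side of the mandible at each visit". Swelling is also taped on both sides. For TPD the section describes the chin site but does not say that both sides are tested.

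**The concern.** Age, skeletal class and genioplasty cannot differ between two rows from the same patient. The documents do not say whether direction and magnitude of movement are recorded once per patient or by side. For a factor fixed within patient, further visits and sides add much less information than the same number of new patients would. Ordinary linear regression treats every row as independent, so pooling the rows overstates precision, and a factor with no effect is too often declared related to recovery.

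The consequence is specific. Participant Recruitment gives the study of age as an influence on healing as one reason for enrolling patients under 18, alongside reaching the sample size. This regression is the only planned analysis that looks at age. As written, the plan permits analyses whose false-positive rate runs from 5% to over 50%, and the choice among them could be made after the data are seen.

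**Working it through.** **The plan's own figure.** The documents give no number for the regression. The nearest is the sample size: difference 0.5, SD 0.5, power 90%. The normal approximation is 2 × (1.960 + 1.282)² × (0.5/0.5)² = 21.01 per arm. The exact two-sided t calculation gives 22.02, hence 23 per arm and 46 in total, as stated. That figure is unaffected by this point.

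**Rows per patient (from Study Design).**
- Visits: day 1 plus weeks 1 to 6 = 7. Adding weeks 8 and 20 gives 9. The pre-operative baseline is not counted.
- Pain: 2 sides × 7 to 9 visits = 14 to 18 rows.
- TPD: 7 to 9 rows, assuming one side.
- Swelling: the index is zero by definition at its baseline visit, given as week 8 in one place and week 6 in another. That leaves 12 to 16 informative rows.

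**If rows are pooled with no patient term.** With m rows per patient and an exchangeable within-patient correlation ICC, for a factor constant within patient:
- design effect DEFF = 1 + (m − 1) × ICC
- true SE / reported SE = √DEFF
- true type I error at nominal two-sided 5% = 2 × [1 − Φ(1.96/√DEFF)]

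The documents give no ICC; 0.2 to 0.6 is an assumption.

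| Outcome | m | ICC | DEFF | √DEFF | Type I error |
|---|---|---|---|---|---|
| TPD | 7 | 0.2 | 2.2 | 1.48 | 19% |
| TPD | 7 | 0.6 | 4.6 | 2.14 | 36% |
| TPD | 9 | 0.2 | 2.6 | 1.61 | 22% |
| TPD | 9 | 0.6 | 5.8 | 2.41 | 42% |
| Swelling | 12 | 0.2 | 3.2 | 1.79 | 27% |
| Swelling | 16 | 0.6 | 10.0 | 3.16 | 54% |
| Pain | 14 | 0.2 | 3.6 | 1.90 | 30% |
| Pain | 14 | 0.6 | 8.8 | 2.97 | 51% |
| Pain | 18 | 0.2 | 4.4 | 2.10 | 35% |
| Pain | 18 | 0.6 | 11.2 | 3.35 | 56% |

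At m = 18 and ICC 0.5, DEFF = 1 + 17 × 0.5 = 9.5. The 46 × 18 = 828 rows then carry the information of 828/9.5 ≈ 87 independent ones, and the type I error is 52%. Pooling only the two sides at one visit (m = 2, ICC 0.3 to 0.7) gives 9-13%.

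**Check by simulation.** 46 patients, six patient-level covariates including arm, 2,000 runs per setting:
- Pooled, 18 rows: 43% at ICC 0.3 and 54% at ICC 0.5.
- Pooled, 9 rows: 30% and 40%.
- One side at one visit: 4.6-6.2%.
- Patient mean: 4.5-5.2%.

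The formula agrees with the simulation, and one row per patient restores the nominal level.

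**If visit-to-visit mean change is left in the residual.** A pooled regression without a visit term has a larger residual variance, so the reported SE grows. As an illustration, assume the variance of the visit means equals the within-visit variance. At m = 18 and ICC 0.5 the ratio halves, 9.5/2 = 4.75, and the type I error falls from 52% to 2 × [1 − Φ(1.96/√4.75)] ≈ 37%.

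**If one regression is run per visit and side.** Each model has one row per patient, and its standard errors are valid. Pain alone then needs 14 to 18 regressions. With five factors and one coefficient each, that is 14 × 5 = 70 to 18 × 5 = 90 coefficients. If no factor matters, 0.05 × 70 = 3.5 to 0.05 × 90 = 4.5 would be expected below 0.05.

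**The case against.** A reader might infer that the standard errors will be too small whatever is done. The documents do not support that, because nothing says rows are pooled. The neighbouring t-tests are run "for the measurements on each side at each time point". If the regression follows that pattern, each model has one row per patient and is valid. A single visit or a patient-level summary is also possible. This objection stands, and it is why the error rates above are conditional. It does not settle the matter: the regression sentence omits the limit its neighbours carry, no summary is named, and the per-visit, per-side reading leaves many coefficients with no order among them.

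Other limits also stand:
- The correlation is assumed, and the formula takes it as exchangeable with stable visit means. Mean change left in the residual reduces the inflation, as shown.
- Two-sided measurement is not established for TPD, so its range uses one row per visit.
- The effect would be smaller for movement magnitude if that is recorded by side.
- The phrase "with alpha set at .05" is attached to the t-tests. Applying 5% to the regression is an assumption.
- The listed factors appear in neither the Hypothesis nor the Outcomes section, so this is a supporting analysis.

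**Conclusion.** The point holds in conditional form. Plain linear regression is named for outcomes repeated within patient, with no unit of analysis and no means of handling the repetition. If visits and sides are pooled, the type I error for patient-level factors is about 30-56% for pain and 19-42% for TPD, assuming an exchangeable correlation of 0.2 to 0.6 and one TPD side, and lower if mean change over visits is left in the residual. If the models are run by visit and side, the error per test is correct, but pain alone has 70-90 coefficients and no rule for which counts.

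A reader might also infer that the trial's main result is at risk. It is not: the laser-versus-placebo comparisons are separate tests made at each time point. The change should still be made, because the two readings closest to the text are either invalid or inefficient and prone to chance findings, and part of the stated reason for enrolling minors rests on this analysis.

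**What to change.** For TPD, VAS pain and swelling index, replace linear regression with one linear mixed model per outcome:
- visit as a factor;
- arm and the listed factors as fixed effects;
- a random intercept for patient, and side within patient where both sides are measured.

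Report each factor's effect with its confidence interval from that model. Omit the swelling baseline visit, after reconciling the week 6 and week 8 statements in Study Design. If the aim is how healing proceeds, rather than the average level across visits, add an age-by-visit term. The yes/no stimulus tests need a binary-outcome model and are outside this change.

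A simpler alternative is acceptable: one pre-specified row per patient for each outcome, at a named visit with sides averaged where both are measured, analysed by ordinary regression.

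Either version takes a few sentences in Data analysis and needs no new data. The mixed model takes slightly more programming, and its intervals will be wider than a pooled regression would report.

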## Background and Significance

Orthognathic surgery is an essential part of correcting dentofacial deformities. The most common surgery for correcting mandibular deformities is the bilateral sagittal split osteotomy (BSSO). The BSSO was first developed in 1957 by Obwegeser(1), and allowed for anteroposterior correction of the mandible in either a Class II or Class III direction. The BSSO has been modified over time to improve surgical stability and reduce negative post-operative sequelae. Despite the modifications, there are still several potential complications that patients may experience. The most common post-operative complications are pain, swelling and nerve dysfunction.

As with any surgery, pain and swelling are unavoidable, but the extent can be variable. A variety of both pharmaceutical and non-pharmaceutical approaches are generally used to improve pain and swelling, including warm compresses, pressure dressings and analgesics. Physical interventions may reduce swelling, which in turn reduces pain, but are limited in their penetration. Meanwhile medications carry their own potential negative consequences; opioids carry a risk for dependence and neutropenia and non-steroidal anti-inflammatories can cause digestive issues, renal problems.

Nerve dysfunction leading to neurosensory deficits are a relatively common side effect of a BSSO, with literature estimating rates between 9% to 84.6% (2, 3) The inferior alveolar nerve (IAN) runs through the mandibular canal in the body of the mandible, with a branch, the mental nerve, splitting off and exiting the bone at the mental foramen between the first and second premolars. The IAN provides sensation to the gingiva and teeth, while the mental nerve provides sensation to the lips and the chin. During the BSSO, the IAN is necessarily moved and is at risk for either direct or indirect injury, which leads to the neurosensory deficits which are usually transient, but can be permanent in some cases (4-7). Therapy for IAN dysfunction is limited.

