### Participant Recruitment

The patient pool for this study will be drawn from regular patients scheduled to undergo orthognathic surgery at Jacobi Medical Center. Patients who have been cleared for orthognathic surgery already must be in good health and understand the risks of the surgery. The only additional requirements for inclusion are 1) the planned surgery includes bilateral sagittal split osteotomies; 2) patients must be free from pre-operative inferior alveolar neurosensory deficiencies; 3) the patient cannot have an intra-operative

accidental fracture or rupture of the inferior alveolar nerve. The details of the whole orthognathic surgery will be recorded (including maxillary procedure, genioplasty, and direction of positional change of the mandible) but will not alter eligibility for enrolment in the study.

Since 2013, over 30% of the patients treated for orthognathic surgery at Jacobi Medical Center are between the ages of 15 and 18, which is in line with orthognathic surgery in general. As such, the study aims to include these patients in the potential pool of subjects. Because of the significant portion of patients under the age of 18 in general, and their inclusion will allow for age to be examined as a related factor in how healing proceeds. Their inclusion will also allow for an adequate sample size.

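### The factor regression uses a linear model for two yes/no nerve tests and leaves out treatment arm, which gives a poor effect scale for those tests and about 11% larger standard errors for the factors

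*Combined protocol and SAP*

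**What the plan says.** The Data analysis section explains that the primary outcome "is measured by the three clinical tests, TPD, soft-stimulus and hard-stimulus". It then gives one sentence to prognostic factors: "Linear regression will be performed to analyze the relationship of the pain, swelling and nerve tests with age, skeletal class, direction and magnitude". Direction and magnitude there refer to the jaw movement, and the last factor named is whether a genioplasty was done. The list stops there, with no term for treatment arm.

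The three nerve tests are on different scales. Under Study Design, for TPD "the first distance felt by the patient as two distinct points will be recorded reported in millimeters". For the other two tests, "The responses will be recorded as positive or negative for soft (swab) or hard pressure (toothpick), by region", over eight regions of the lower face. No summed score is defined. For the comparison between arms, the plan treats these two tests as categorical: "The soft- and hard-stimulus tests for each region will be analyzed at each time point with a chi-square test".

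Background and Significance describes the operation as allowing "anteroposterior correction of the mandible in either a Class II or Class III direction". Participant Recruitment gives the regression a purpose. Among the reasons for enrolling patients under 18 is that "their inclusion will allow for age to be examined as a related factor in how healing proceeds".

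**The concern.** Three features of the regression sentence deserve attention.

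- **Outcome type.** The nerve tests include two yes/no outcomes. A straight line fitted to a 0/1 result can predict impossible values, and it expresses effects on a scale that behaves badly when nearly everyone responds.
- **Missing arm.** The trial is planned around a treatment difference of one standard deviation. If arm is left out, that difference becomes unexplained variation and makes every factor effect harder to see.
- **Overlapping factors.** Skeletal class and direction of movement may carry much the same information.

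At stake is how well the trial can answer the question about age and healing, which the plan uses as one reason for including minors. No other analysis in the plan addresses it.

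**Working it through.** **Inputs.** Sample Size gives a difference of 0.5, SD 0.5, 90% power and 23 per arm (46 in total). Data analysis gives alpha 0.05, taken here as two-sided. The documents do not give positive-response rates, factor slopes, within-patient correlation or the overlap of class and direction, so values for these are assumptions.

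**1. The plan's own figure.** The standardised difference is 0.5/0.5 = 1.0. A two-sample t-test at two-sided 0.05 and 90% power needs 22.02 per arm, so 23. The stated figure is reproduced, and the planning values can be carried into step 2.

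**2. Omitting arm.** With equal arms, the treatment difference adds (difference²)/4 to the residual variance:

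- 0.5²/4 = 0.0625
- 0.25 + 0.0625 = 0.3125, and 0.3125/0.25 = 1.25, a rise of 25%
- residual SD √0.3125 = 0.559 against 0.500, a ratio of 1.118

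A simulation of 46 patients (5,000 runs, true age slope assumed at 0.2 per SD) gave:

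| | Arm omitted | Arm included |
|---|---|---|
| Mean age coefficient | 0.201 | 0.200 |
| Standard error | 0.087 | 0.079 |
| Power | 61% | 69% |

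The unrounded standard errors are 0.0874 and 0.0790, a ratio of 1.11. With arm omitted and no true age effect, type I error was 4.8%. The loss is in precision, with no bias.

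**3. Linear model on a yes/no result.** This was simulated with one result per patient and 46 patients. Type I error for age was estimated with no true factor effects. Fitted values were examined with an assumed log-odds slope of 0.8 per SD for one factor.

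| Positive rate (assumed) | Type I error | Fitted values outside 0 to 1 |
|---|---|---|
| 50% | 5.6% | 3% |
| 80% | 5.2% | 9% |
| 90% | 5.3% | 16% |
| 95% | 5.4% | 23% |

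The test of no effect holds its level. The fitted values do not stay in range, and the problem grows as more patients respond.

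**4. Class and direction in one model.** Assume both are two-level, with class split 23/23. The variance inflation factor is 1/(1 − r²), and its square root multiplies the standard error. With two discordant patients, one each way, r = (22 × 22 − 1 × 1)/(23 × 23) = 483/529 = 0.913.

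| Discordant of 46 | r | Variance inflation | Standard error multiplied by |
|---|---|---|---|
| 0 | 1 | not estimable | not estimable |
| 1 | 0.957 | 12.0 | 3.5 |
| 2 | 0.913 | 6.0 | 2.5 |
| 4 | 0.826 | 3.1 | 1.8 |
| 8 | 0.652 | 1.7 | 1.3 |

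This affects those two coefficients only.

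**5. Which replacement is safe.** A plain binomial model on the count of positive regions treats a patient's eight regions as independent. With within-patient correlation ρ, the variance is understated by a factor of 1 + 7ρ, and type I error is about 2[1 − Φ(1.96/√(1 + 7ρ))]:

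- ρ = 0.1: factor 1.7, 1.96/1.304 = 1.503, type I error about 13%
- ρ = 0.3: factor 3.1, 1.96/1.761 = 1.113, type I error about 27%

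Simulation agrees, with 12% to 14% and 26% to 28%. Linear regression on each patient's proportion of positive regions stayed at 4.8% to 5.4%. A plain binomial model would therefore be worse than the present plan.

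**The case against.** The strongest reply is that little harm follows. Linear regression suits TPD, VAS and the swelling index in type. The regression is a supporting analysis, since the arms are compared by t-tests and chi-square tests. Most of this stands, and it rules out four stronger readings that a reader might take from the text.

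- **Factor effects confounded with treatment.** Randomisation rules this out on average. A single allocation can still be uneven: a gap of 20 points or more between arms in genioplasty has a probability of about 14% to 19% (30% to 50% genioplasty, assumed). Such a gap would move the genioplasty coefficient by about 0.2 × 0.5 = 0.1. The sampling SD of that coefficient is about 0.17 (40% genioplasty assumed), so the shift is about 0.6 of a standard error. The standard error already covers chance imbalance of this kind. Including arm would remove it, which is a gain in precision.
- **Invalid standard errors for the sensory tests.** With one result per patient, type I error stays near 5%. The published deficit rates in Background and Significance, 9% to 84.6%, vary between studies. They do not show how far probabilities vary between patients in this trial.
- **Class and direction are the same variable.** The background sentence says what the operation permits. Participant Recruitment records direction of mandibular change as a surgical detail, alongside any maxillary procedure, so class need not determine it. The plan also does not say that the factors share one model. In separate models the problem does not arise.
- **All the factor results are unreliable.** The outcome mismatch concerns two tests, and the overlap concerns two coefficients. Age is not touched by the overlap.

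The reply does not remove the mismatch itself: the plan treats the swab and toothpick tests as categorical in one sentence and fits a line to them in another. Nor does it give a reason for leaving out arm.

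**Conclusion.** The point holds as a minor one. For the swab and toothpick tests the linear model is poorly matched to the data. The consequence is out-of-range fitted values and a poor effect scale, with no demonstrated inflation of false positives when each patient contributes one result.

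Omitting arm costs 25% in residual variance and about 11% in factor standard errors. For the assumed age slope, power is 61% instead of 69%. These figures depend on the planning difference and SD, so they apply to the outcome those values describe. The plan gives no such values for VAS, swelling or the binary tests. A smaller treatment effect would mean a smaller loss.

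The class and direction point is conditional on a joint model and on an overlap that the documents do not state. The remaining factors and the treatment comparison are unaffected.

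**What to change.** In the Data analysis section:

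1. Keep linear regression for TPD, VAS and the swelling index.
2. For the swab and toothpick tests, use an ordinal model on each patient's number of positive regions, or a logistic model on region-level results that allows for within-patient correlation (GEE or a patient random effect). Do not use a plain binomial model on the count.
3. Include treatment arm in every model.
4. Cross-tabulate skeletal class against direction of movement, and do not enter both in one model if they largely coincide.
5. State whether factors are fitted jointly, which visit is used, and how the two sides and repeated visits are handled. The models in items 1 and 2 cannot be fitted without this.

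The cost is analysis wording and slightly more analysis work. Arm, the region-level results and the listed factors are already part of the plan, so no new data collection is needed.
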